8.3 Efficacy Analyses

8.3.1 Primary Efficacy Endpoints

The primary efficacy endpoint, objective response evaluated by IRRC, refers to CR or PR determined by IRRC based upon Lugano 2014 classification. For subjects who fail to meet the above criteria or fail to receive any tumor assessment after baseline will be considered as non-responder.

ORR is the rate of objective responders. The population involved in the IRRC-ORR analysis are EAS subjects with evaluable or measurable lesion at baseline confirmed by IRRC.

The 95% confidence interval (CI) of ORR will be calculated using the exact binomial (Clopper-Pearson) method to evaluate the precision of the ORR estimate.

The statistical analysis will be performed by 24 weeks after the first dose of the last subject.

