8.3.2 Secondary Efficacy Endpoints

Proportions of subjects who achieve CR, PR, SD, and PD per IRRC evaluation and their 95% CIs will be summarized. This analysis will be performed in EAS subjects with evaluable or measurable lesion at baseline judged by IRRC. Proportions of subjects with responses per investigator's evaluation and their 95% CIs will be summarized. This analysis will be performed in EAS subjects with evaluable or measurable lesion at baseline judged by investigators.

Duration of response (DoR) is defined as the time from the first documented CR or PR (whichever comes first) to the first documented disease progression or death, whichever comes first. DoR will be evaluated in subjects with objective responses per investigator's or IRRC's assessment, respectively. At analysis, subjects without event (disease progression or death) as of data cutoff will be censored at the date of "last tumor assessment". If no tumor assessment is performed after the first occurrence of CR or PR, DoR will be censored at the date when CR or PR first occurs. Kaplan-Meier method will be used to analyze DoR; the KM curve will be constructed.

Time to response (TTR) is defined as the time from the first study dose to the first documented CR or PR, whichever comes first. TTR will only be evaluated for subjects who achieve ORR. TTR will be summarized according to the investigator's and IRRC's assessments, respectively.

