8.7 EXPLORATORY ANALYSES

Progression-free survival (PFS) and overall survival (OS) will be explored. PFS is defined as the time from the first study dose to the date of first documented disease progression or death, whichever comes first. The investigators and IRRC will assess the progression of disease based upon the Lugano 2014 classification. At the analysis, subjects without event (disease progression or death) will be censored at the date of "last tumor assessment". Subjects without tumor assessment after baseline will be censored at the date of the first dose. Six-month PFS rate refers to the proportion of subjects who are alive without any progression at 6 months after the first dose of investigational product. Six-month PFS rate will be calculated using the Kaplan-Meier method and the Greenwood formula was used to derive the variance regarding its 95% CI calculation.

OS is defined as the time from the first study dose to the date of death irrespective of its cause. Subjects without death reports as of data cutoff will be censored at the date of the last survival confirmation. Subjects without any data after baseline will be censored at the date of the first dose. The same analysis method is used for PFS.

Exploratory biomarker analysis will be performed to identify the relationship between tumor genetic aberrations and the efficacy of the investigational product. Subjects will be subgrouped based upon their demographics (for example age, sex) and baseline characteristics (for example ECOG PS, prior treatment lines) for evaluating the consistency among all subgroups.

The consistency of ORR (yes or no) between IRRC evaluation and investigator's evaluation will also be assessed.

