The primary efficacy endpoint is ORR by IRRC based upon Lugano 2014 classification, defined as the proportion of subjects who achieve complete response (CR) or partial response (PR) as the best overall response. Subjects who did not have any post-baseline tumor assessment will be considered as non-responders.

The IRRC-ORR analysis will include subjects with evaluable or measurable lesion at baseline as confirmed by IRRC in EAS.

The 95% CI of ORR will be calculated using the exact binomial (Clopper-Pearson) method to evaluate the precision of the ORR estimate.

Secondary Efficacy Endpoints

The ORR assessed by investigators will be analyzed and provided as described in Section 0. Proportions of subjects who achieve CR, PR, stable disease (SD), and progressive disease (PD) per IRRC evaluation and their 95% CIs will be summarized. This analysis will be performed for subjects with evaluable or measurable lesion at baseline as confirmed by IRRC in EAS. Proportions of subjects with responses per investigator's evaluation and their 95% CIs will also be summarized as for IRRC. This analysis will be performed for subjects with evaluable or measurable lesion at baseline as confirmed by investigators in EAS.

Duration of response (DoR) is defined as the time from the first documented CR or PR (whichever comes first) to the first documented disease progression or death, whichever comes first. DoR will be evaluated in subjects with objective responses per investigator's or IRRC's assessment, respectively. Subjects without event (disease progression or death) as of data cutoff will be censored at the date of the last tumor assessment. If no tumor assessment is performed after the first occurrence of CR or PR, DoR will be censored at the date of first CR or PR. Subjects with subsequent anti-cancer therapy(if any) before event will be cencored at the date of last tumor assessment prior to the initiation of therapy. If an event is observed immediately after two or more consecutive missed tumor assessments, subjects will be censored at the date of last tumor assessment prior to the missing tumor assessments. Kaplan-Meier methodology will be used to analyze DoR and the KM curve will be constructed.

Time to response (TTR) is defined as the time from the first study dose to the first documented CR or PR, whichever comes first. TTR will only be evaluated for subjects

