who achieve a response. TTR will be summarized according to the investigator's and IRRC's assessments, respectively.

Progression-free survival (PFS) in months is defined as the time from the date of the first dose to the date of first documented disease progression or death, whichever comes first. The investigators and IRRC will assess the progression of disease based upon the Lugano 2014 classification. Subjects without an event (disease progression or death) will be censored at the date of the last tumor assessment. Subjects without tumor assessment after baseline will be censored at the date of the first dose. 6-month PFS rate refers to the proportion of subjects who are alive without any progression or death at 6 months after the first dose of study drug. 6-month PFS rate will be calculated using the Kaplan-Meier method and the Greenwood formula will be used to derive the variance for the 95% CI calculation.

Overall survival (OS) is defined as the time from the date of the first dose to the date of death from any cause. Subjects without death will be censored at the date of the last date known to be alive. Subjects without any data after baseline will be censored at the date of the first dose. The detailed analysis methodology described for PFS will also be used for the analysis of OS.

Sensitivity Analyses

The IRRC-ORR analysis will be repeated for subjects in the safety analysis set.

Subgroup Analyses

Subjects will be grouped based upon their demographics (for example age, sex) and baseline characteristics (for example ECOG PS, prior treatment lines) to evaluate the consistency among all subgroups

Exploratory Analyses

Exploratory analysis will be performed to identify the relationship between biomarkers and the efficacy of the study drug. The consistency of ORR (yes or no) between IRRC evaluation and investigator's evaluation will also be assessed.

PHARMACOKINETIC AND PHARMACODYNAMIC ANALYSES

Pharmacokinetic Analyses

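### Must the plan say whether a response first seen after Lugano progression counts toward best overall response?

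*Protocol*

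**What the plan says.** Protocol 8.3.1 states that "objective response evaluated by IRRC, refers to CR or PR determined by IRRC based upon Lugano 2014 classification". Its non-responder rule reads: "For subjects who fail to meet the above criteria or fail to receive any tumor assessment after baseline will be considered as non-responder". The term best overall response is not used in 8.3.1. It appears in the protocol synopsis and in the SAP's Primary Efficacy Endpoint section, where ORR is "defined as the proportion of subjects who achieve complete response (CR) or partial response (PR) as the best overall response".

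The linked endpoints are worded as follows.

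- **TTR** (Protocol 8.3.2): "Time to response (TTR) is defined as the time from the first study dose to the first documented CR or PR, whichever comes first".
- **DoR** (Protocol 8.3.2) runs from first CR or PR "to the first documented disease progression or death, whichever comes first". The SAP adds that "DoR will be evaluated in subjects with objective responses per investigator's or IRRC's assessment, respectively".
- **PFS** (Protocol 8.7) runs from first dose "to the date of first documented disease progression or death, whichever comes first". The SAP defines it in the same way: "as the time from the date of the first dose to the date of first documented disease progression or death, whichever comes first".

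Protocol 3.1.2.1 lets a subject with Lugano progression stay on drug and be re-imaged if pseudo-progression is suspected and, in special situations, after confirmed progression. The SAP's section on the independent radiological review committee describes double reads, a global review that may revise earlier timepoint calls, adjudication and an oncology review. It refers to the IRRC charter for further detail.

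**The concern.** The protocol expects some subjects to progress on imaging and then respond. Section 3.2.4 gives this as the reason for treating past progression, and section 1.1 cites one such patient among seven in a pembrolizumab series. Yet no sentence says whether best overall response closes at first progression, at confirmed progression or at new therapy. A subject with progression and then PR belongs to neither non-responder group named in 8.3.1, so a literal reader would count that subject as a responder. A programmer who stops at first progression would not.

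The responder set feeds ORR, TTR and DoR. It also sets the SAP's repeat analysis for US filing, which waits until every responder has six months of follow-up from first response. If the set were left open until data had been seen, the choice could be influenced by the results. The same words about first documented progression also close both PFS and DoR, and for such a subject they must point to different dates.

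**Working it through.** The plan gives no figure for this point, so there is none to reproduce. The check has three parts.

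**1. Can the sequence occur?** Protocol 6.4 schedules PET/CT at Weeks 12 and 24. In Appendix 13.1 the PET criteria for both PR and progression by uptake compare with baseline, so progression at Week 12 and PR at Week 24 can be coded. Two points narrow this. Progression by a new lesion cannot become PR while that lesion persists. The SAP bases the IRRC call on CT/MRI and PET together, and CT progression is measured from nadir, so the PET comparison is only part of the assessment.

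**2. What do the definitions give?** Take progression at Week 12, PR at Week 24 and progression at Week 48.

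- PFS: event at Week 12 under either document. This is simply the stated definition.
- If the PR counts: TTR = 24 weeks.
- DoR read literally to the first progression ever recorded: 12 − 24 = −12 weeks, which is not a duration.
- DoR read forward from response: 48 − 24 = 24 weeks.
- If best response closes at first progression: best response is progression, and TTR and DoR do not arise.

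The DoR censoring text looks only at assessments after the first CR or PR, so it already reads forward. The fact that TTR + DoR (24 + 24 = 48) differs from PFS (12) shows no error. Neither document states that identity, and the SAP already breaks it for ordinary responders: DoR is censored for new therapy and for two or more missed assessments, while the PFS text has neither rule.

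**3. How large could the effect be?** Inputs: about 80 subjects (protocol synopsis and section 4), exact Clopper-Pearson 95% limits (8.3.1), and a historical control of 20% (3.2.3). The ORR values, and the analysed numbers 75 and 70, are assumptions. One subject moves ORR by 100/n: 1.25 points at n = 80, 1.33 at 75, 1.43 at 70.

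The lower limit is the 0.025 quantile of Beta(x, n − x + 1). At n = 80, 24 responders give 20.3% and 23 give 19.2%. So x − 23 responders must be removed before the lower limit falls below 20%.

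| Responders of 80 (assumed) | ORR | Exact 95% CI | Removals needed |
|---|---|---|---|
| 24 | 30.0% | 20.3 to 41.3% | 1 |
| 26 | 32.5% | 22.4 to 43.9% | 3 |
| 28 | 35.0% | 24.7 to 46.5% | 5 |
| 32 | 40.0% | 29.2 to 51.6% | 9 |
| 36 | 45.0% | 33.8 to 56.5% | 13 |

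At 40% with smaller sets: for n = 75, 30 responders need 8 removals (23/75 lower limit 20.5%, 22/75 19.4%). For n = 70, 28 responders need 7 (22/70 20.9%, 21/70 19.6%).

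The only frequency cited in the protocol is 1 of 7 responders, for another drug; its exact 95% CI is 0.4 to 57.9%, so it says very little. Applied as it stands:

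- 26 responders: 26/7 = 3.7, about 4 removed, leaving 22/80 (27.5%, CI 18.1 to 38.6%).
- 28 responders: 28/7 = 4 removed, leaving 24/80 (30.0%, CI 20.3 to 41.3%).
- 32 responders: 32/7 = 4.6, about 5 removed, leaving 27/80 (33.8%, CI 23.6 to 45.2%).

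On that assumption, the position against 20% turns on this choice only when ORR is in the low thirties or below.

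**The case for a change.** The best case for a change is that an unstated convention is not a pre-specified rule, and that this protocol treats past progression on purpose. The SAP cites particular charter sections for adjudication (7.1), per-visit oncology assessment (8.7) and secondary review (12.1), but none for the window of best response. Global review permits revision of an early progression call without requiring it. Neither safeguard reaches investigator-assessed ORR and DoR, which are secondary endpoints. For those, Protocol 6.4 cites the site radiology manual only for imaging. The remedy would cost a sentence or a citation. If the observed count fell at 24 of 80, one subject would move the lower limit across 20%.

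Most of this stands as description: the sentence is missing, and for the investigator endpoints nothing visible supplies it. It does not show that the primary endpoint lacks a rule, because the charter and the review workflow diagram are not available to read. Nor does it show that a post-progression responder must be counted. The protocol asks for routine tumor assessment up to radiological progression, new anti-cancer treatment, death or end of trial (3.1.3, 4.3.2, 6.4). That is an imaging schedule and not a response rule, but it confines the open question to subjects imaged under the 3.1.2.1 exception. The 24-of-80 case is one point in the table, and the public text shows no decision rule that it would trip.

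The repeat-analysis trigger adds nothing. A counted Week 24 response in the last subject sets it at 24 + 26 = 50 weeks after that subject's first dose (six months taken as 26 weeks), but so does any ordinary first response at Week 24.

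**Conclusion.** No change follows. The documents leave one detail unstated, and analysts would ordinarily fill it by taking best response up to first progression or new therapy, while reporting any later response descriptively. Per-visit assessments are collected in any case, so either count can be derived from the same data. The DoR wording is loose, but only the forward reading gives a usable duration, and the censoring text supports it.

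The size is 1.25 points of ORR per affected subject at n = 80. The number affected is unknown and probably small, since it needs a subject kept on drug after progression who then responds and whose progression call survives review. At an assumed 40% ORR it would take 9 of 32 responders to alter the position against 20%. At 35% it would take 5 of 28, and only near 30% would one or a few suffice.

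This rests on three assumptions: that the charter or global review handles the IRRC case sensibly, that about 70 to 80 subjects are analysed, and that the 20% figure serves as a reference, since no formal test against it is visible. No result or conclusion is shown to be wrong under the plan as written, and asking for the window to be stated would not in itself select a better rule.

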8.3.2 Secondary Efficacy Endpoints

Proportions of subjects who achieve CR, PR, SD, and PD per IRRC evaluation and their 95% CIs will be summarized. This analysis will be performed in EAS subjects with evaluable or measurable lesion at baseline judged by IRRC. Proportions of subjects with responses per investigator's evaluation and their 95% CIs will be summarized. This analysis will be performed in EAS subjects with evaluable or measurable lesion at baseline judged by investigators.

Duration of response (DoR) is defined as the time from the first documented CR or PR (whichever comes first) to the first documented disease progression or death, whichever comes first. DoR will be evaluated in subjects with objective responses per investigator's or IRRC's assessment, respectively. At analysis, subjects without event (disease progression or death) as of data cutoff will be censored at the date of "last tumor assessment". If no tumor assessment is performed after the first occurrence of CR or PR, DoR will be censored at the date when CR or PR first occurs. Kaplan-Meier method will be used to analyze DoR; the KM curve will be constructed.

Time to response (TTR) is defined as the time from the first study dose to the first documented CR or PR, whichever comes first. TTR will only be evaluated for subjects who achieve ORR. TTR will be summarized according to the investigator's and IRRC's assessments, respectively.

8.4 SAFETY ANALYSES

The safety analysis will be performed for the SAS population.

Descriptive statistics will be performed to summarize the exposure of the investigational product, which may contain number of cycles, administrations and dose levels, etc.

All adverse events will be described according to MedDRA and graded according to the NCI CTCAE v4.03. All adverse events that occurred during or after investigational product administration will be summarized by NCI CTCAE grade. In addition, serious adverse events, severe adverse events (Grade 3, 4, or 5 events), drug-related AEs, and AEs causing discontinuation or dose modification of the investigational product will each be summarized. Multiple occurrences of the same event will be only counted once for the most severe event. The proportion of subjects with more than one adverse event will be reported.

All deaths that occur during the study or within the defined follow-up period after the last dose/discontinuation of investigational product will be reported.

Specific laboratory tests, vital signs, physical examinations, and 12-lead ECGs and their changes compared with baseline will be summarized. The values at baseline and each time point post-baseline will be presented by crosstabs, when appropriate.

8.5 PHARMACOKINETIC ANALYSES

Descriptive analysis will be performed for serum concentration of CS1001 in samples taken planned sampling time points. The data in this study will be pooled with that from other CS1001 trials to develop a population PK model. This model will be used to evaluate internal and external covariates and their influence on the PK of CS1001. Furthermore, the exposure-response analysis will be performed on specific efficacy and safety endpoints. Results of the above group PK and exposure-response analyses will be recorded in separate reports.

8.6 IMMUNOGENICITY ANALYSES

Immunogenicity evaluation results will be reported for the following parameters. Number and percentage of subjects who have positive ADA at baseline; number and percentage of subjects with at least one positive ADA test result in any time point following the first dose of the investigational product; number and percentage of subjects who develop treatmentinduced ADA anytime after the first dose of the investigational product; number and percentage of subjects with treatment-enhanced ADA anytime after the first dose of investigational product. The treatment-induced ADA will also be analyzed by computing and reporting duration of an induced ADA response which will be classified as transientpositive ADA or persistent-positive ADA.

8.7 EXPLORATORY ANALYSES

Progression-free survival (PFS) and overall survival (OS) will be explored. PFS is defined as the time from the first study dose to the date of first documented disease progression or death, whichever comes first. The investigators and IRRC will assess the progression of disease based upon the Lugano 2014 classification. At the analysis, subjects without event (disease progression or death) will be censored at the date of "last tumor assessment". Subjects without tumor assessment after baseline will be censored at the date of the first dose. Six-month PFS rate refers to the proportion of subjects who are alive without any progression at 6 months after the first dose of investigational product. Six-month PFS rate will be calculated using the Kaplan-Meier method and the Greenwood formula was used to derive the variance regarding its 95% CI calculation.

OS is defined as the time from the first study dose to the date of death irrespective of its cause. Subjects without death reports as of data cutoff will be censored at the date of the last survival confirmation. Subjects without any data after baseline will be censored at the date of the first dose. The same analysis method is used for PFS.

Exploratory biomarker analysis will be performed to identify the relationship between tumor genetic aberrations and the efficacy of the investigational product. Subjects will be subgrouped based upon their demographics (for example age, sex) and baseline characteristics (for example ECOG PS, prior treatment lines) for evaluating the consistency among all subgroups.

The consistency of ORR (yes or no) between IRRC evaluation and investigator's evaluation will also be assessed.

8.8 HANDLING OF MISSING DATA

Subjects without any assessment after baseline will be regarded as non-responders at ORR analysis.

Subjects without available data on the date of disease progression or death when calculating PFS will be censored at the date of the last tumor assessment. Subjects without any tumor assessment after the baseline will be censored at the date of the first dose.

Subjects without death report at OS analysis will be censored at the date of the last survival confirmation. For OS analysis, subjects without any data after baseline will be censored at the date of the first dose.

For DoR analysis, subjects without event (no disease progression or death) by database locking will be censored at the date of "last tumor assessment". If no tumor assessment is performed after the first occurrence of CR or PR, DoR will be censored at the date of the first occurrence of CR or PR first occurs.

